7.6.2.3 Thyroid Function Tests

- TSH, T3 free, T3 total, T4 free, T4 total on Durva+Treme (**Table 51**)
- Overall TSH, T3 free, T3 total, T4 free, T4 total (**Table 52**)

7.6.2.3 Coagulation

- PT, INR, PTT on Durva+Treme (**Table 53**)
- Overall PT, INR, PTT (**Table 54**)

7.7.3 Other Safety

7.6.3.1 ECG

Cardiac function of patients is evaluated as clinically indicated by ECG during protocol treatment for patients on Durva+Treme with results reported on Treatment Report and before progression for patients on BSC with results reported on Best Supportive Care Report.

- Overall number of patients by normal or abnormal ECG, by treatment group (**Table 55**)

7.6.3.2 Urinalysis

Dipstick urinalysis is performed as clinically indicated during protocol treatment for patients on Durva+Treme with results reported on Treatment Report and before progression for patients on BSC with results reported on Best Supportive Care Report.

- Results of urinalysis, by treatment group (**Table 56**)

7.7.4 Deaths on Study/Adverse Events Leading to Discontinuations of Protocol Treatment

- Deaths during durvalumab and tremelimumab treatment or within 4 weeks of last durvalumab and tremelimumab treatment (DURVA+TREME Arm only): number of patients who died and cause of death from Date/Cause of Death Section of Death Report (**Table 57**)
- Number of patients with adverse events leading to discontinuations of durvalumab as identified from Off Protocol Treatment - Adverse Events of End of Treatment Report (DURVA+TREME Arm only) (**Table 58**)
- Number of patients with adverse events leading to discontinuations of tremelimumab as identified from Off Protocol Treatment - Adverse Events of End of Treatment Report (**Table 58**)

7.8 Concomitant Medications, Other Anti-Cancer Treatments, and Major Medical Problems

Investigators may prescribe concomitant medications or treatments deemed necessary to provide adequate prophylactic or supportive care. Administration of any other anti-cancer therapy is not permitted while the patient is receiving protocol therapy.

Thereafter, patients may be treated at the investigator’s discretion. Major medical problems are those thought unrelated to protocol treatment.

- Concomitant medications for patients on DURVA+TREME Arm during or 4 weeks after Durvalumab and Tremelimumab Treatment (reported on Treatment Report and 4-Week Post-Treatment Follow-Up Report) and on BSC Arm prior to objective disease progression (reported on Best Supportive Care Report) (**Table 59**)
- Anti-cancer treatments during or 4 weeks after Durvalumab and Tremelimumab Treatment (reported on Treatment Report and 4 Weeks 4-Week Post-Treatment Follow-Up Report) (DURVA+TREME Arm only) (**Table 60**)
- Anti-cancer treatments before progression (reported on Treatment Report 4-Week Post-Treatment Follow-Up Report, and Follow-up Report for patients on DURVA+TREME Arm and Best Supportive Care Report on BSC), by treatment group (**Table 60**)
- Anti-cancer treatments for all patients after progression (reported on Short Follow-up Report), by treatment group (**Table 60**)
- Major medical problem before progression (reported on Treatment Report 4-Week Post-Treatment Follow-Up Report, and Follow-up Report for patients on DURVA+TREME Arm and Best Supportive Care Report on BSC), by treatment group (**Table 61**)

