5.2 Patient Evaluation Flowsheet: Pre-Treatment, On-Study, and after Protocol Treatment
 For Patients Randomized to Durvalumab and Tremelimumab (Arm 2)

| Required Investigations | PRE-STUDY (≤14 days prior to randomization, unless otherwise indicated) | DURING Protocol Treatment Day 1 each cycle, and as clinically indicated (unless otherwise indicated) | AFTER Protocol Treatment is Permanently Discontinued ¹ | | | |
|---|--|---|---|--------------------------|---|---------------------------|
| | | | PRIOR to objective disease progression | | AFTER objective disease progression | |
| | | | 4 weeks after end of last cycle date | Every 4 weeks thereafter | 4 weeks after end of last cycle date ¹ | Every 12 weeks thereafter |
| History and Physical Exam² | | | | | | |
| Including: height (baseline only), weight, ECOG performance status, clinical tumour measurements (if applicable) | X | X | X | X | X | |
| Vital Signs (blood pressure, heart rate, temperature) | X | X ³ | | | | |
| Concomitant Medications | X | X | X | | X | |
| Overall Survival | | | | | | |
| Survival status assessment | | X | X | X | X | X ⁴ |
| Hematology^{2,5} | | | | | | |
| CBC, differential (including lymphocytes), platelets | X | X ² | X | X | X | X ⁵ |
| Coagulation^{2,5} | | | | | | |
| PTT, PT/INR | X | X ² | X | X | X | X ⁵ |
| Biochemistry^{2,5} | | | | | | |
| Serum Creatinine, Chloride, Sodium, Potassium, Calcium, Magnesium, Bilirubin, ALP, AST and ALT, LDH, Albumin, TSH ⁶ , Amylase, Lipase, Serum CEA | X | X ² | X | X | X | X ⁵ |
| Creatinine Clearance (calculated) | X | as clinically indicated | | | | |
| Glucose | X | as clinically indicated | | | | |
| Radiology⁷ | | | | | | |
| Chest/abdomen/pelvis CT or MRI scan | X ≤ 28 days | X ⁷ Every 8 weeks from randomization until objective disease progression (maintain schedule even if cycles are delayed) | | | | |
| Other scans as necessary to document all measurable and non-measurable disease | X ≤ 28 days | | | | | |
| Other Investigations | | | | | | |
| Pregnancy Test ⁸ | X | | | | | |
| ECG | X | as clinically indicated | | | | |
| Dipstick Urinalysis (including protein, specific gravity, glucose and blood) | X | | | | | |

table continued on next page ...

ADMIN UPDATE #1: 2018-JAN-24

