7.1.7 Duration of Therapy

In the absence of unequivocal disease progression, as defined in Section 10.2.5, intolerable toxicity or withdrawal of consent to further participation, patients may continue to receive study treatment of durvalumab and tremelimumab at the discretion of the Investigator.

If, in the opinion of the Investigator, a patient is deriving clinical benefit from study therapy despite the documentation of objective disease progression per RECIST 1.1 criteria, then provided the patient does not have any significant, unacceptable, or irreversible toxicities that indicate that continuing treatment will not further benefit the patient, the patient may remain on study therapy pending their next disease assessment. However, appropriate imaging studies must be repeated within 4-8 weeks to re-assess treatment response. A patient with objective disease progression confirmed on subsequent assessment by either RECIST 1.1 criteria or Immune-Related Response criteria (irRC) as appropriate should be discontinued from the study. Patients should also be discontinued from the study if objective disease progression occurs in a target lesion that has previously shown a confirmed response.

For a complete list of general criteria for stopping study treatment, please see Section 10.0.

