APPENDIX IV - DOCUMENTATION FOR STUDY

Follow-up is required for patients from the time of randomization and will apply to all eligible patients.

This trial will use a web-based Electronic Data Capture (EDC) system for all data collection. For details of accessing the EDC system and completing the on-line Case Report Forms please refer to the “CCTG EDC Generic Data Management Guidebook” posted on the CO.26 area of the CCTG web-site (www.ctg.queensu.ca).

The electronic CRFs to be used in this trial, through the EDC system, are as follows:

| Electronic Folder | Timing | To be completed electronically | Supporting Documentation Required ¹ |
|---|--|--|--|
| Eligibility Checklist | | At the time of randomization | 
 • consent form² |
| Baseline Report | | Within 2 weeks of randomization | 
 • relevant pathology report(s) • RAS reports • relevant operative report(s) • relevant radiology reports (including CT/MRI abdomen/pelvis, CT/MRI chest, chest x-ray) • tumour measurement worksheet • ECG report |
| Correlative Studies Report (Tumour and Blood) | Continuous running-log folder See Section 5.0 | Information pertaining to tumour tissue submission must be completed as soon as possible after randomization, and tissue submitted within 4 weeks of randomization. | 
 • Consent form² • Diagnostic pathology report (for tumour tissue only) |
| | | Information pertaining to baseline/pretreatment blood collection for correlative studies (i.e. whole blood, plasma, serum) must be completed within 2 weeks of randomization. | |
| | | Information pertaining to post randomization blood collection samples (i.e. whole blood, plasma, serum) for correlative studies and banking should be completed within 2 weeks after collection of blood specimens. | |
| Concomitant Medication Report | Continuous running-log folder | | |
| Best Supportive Care Report (Arm 1 only) | Every 4 weeks (28 days) until objective progression | Within 2 weeks of the end of each reporting period | 
 • If available/applicable: • CT/MRI abdomen/pelvis report • CT/MRI chest • other radiology reports • tumour measurement worksheet • ECG report |

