| Treatment Report (Arm 2 only) | Every 4 weeks (28 days) while patient is on protocol treatment | Within 2 weeks of the end of each 4 week reporting period | If available/applicable: 
 • CT/MRI abdomen/pelvis report • CT/MRI chest • other radiology reports • tumour measurement worksheet • ECG report |

table continues on next page ...

| Electronic Folder | Timing | To be completed electronically | Supporting Documentation Required ¹ |
|--|---|---|--|
| End of Treatment Report(Arm 2 only) | As soon as permanent off treatment status is confirmed. | Within 2 weeks of end of treatment | |
| 4-Week Post-Treatment Follow-Up Report (Arm 2 only) | 4 weeks from the date of last infusion | Within 2 weeks of the 4-week post treatment follow up visit | 
 • relevant radiology reports |
| Follow-up Report ³ (Arm 2 only) | Every 4 weeks (28 days) until objective progression | Within 2 weeks of follow-up visit | If available/applicable: 
 • CT/MRI abdomen/pelvis report • tumour measurement worksheet • CT/MRI chest report • other radiology reports • ECG report |
| Short Follow-up Report | Every 12 weeks after objective disease progression | Within 2 weeks of follow-up visit | |
| Relapse/Progression Report | Upon the patient's objective disease progression / relapse | Within 4 weeks of confirmation | 
 • relevant radiology, operative and pathology reports |
| Death Report | Upon patient's death | Within 4 weeks of patient death | 
 • autopsy/post-mortem report, if performed |
| Serious Adverse Event (SAE) Report ⁴ | Within 24 hours of event At time of event and reported to CCTG | Within 1 working day ⁴ | |
| Minimal Follow-up Report ⁵ | Annual | Within 6 weeks of contact | If available/applicable: 
 • autopsy report • CT/MRI report |

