7.6.3 Progression-free Survival

Progression-free survival (PFS) will be calculated for all patients from the day of randomization until the first observation of disease progression (date of objective relapse or progression of Relapse/Progression Report) or death due to any cause (recorded in Date/Cause of Death Section of Death Report) as the (difference+1).

If a patient has not progressed or died, PFS will be censored on the date of last disease assessment defined as the earliest test date of target lesion or non-target lesions (if patient has no target lesions), whichever is latest.

A frequency table will be provided describing progression and censoring as follows (**Table 35**):

- Number of patients who progress (documented progression, death without documented progression)
- Number of patients censored (alive and not progressed)

Analyses for PFS will be similar to that for overall survival as previously described. A Kaplan-Meier curve for PFS in each treatment arm will be displayed (**Figure 3**). In the primary analysis, median PFS for the two treatments will be compared using the stratified log-rank test (**Table 36**). A stratified Cox regression model will estimate the durvalumab and tremelimumab combined with best supportive care (ARM 2) over best supportive care alone (ARM 1) PFS hazard ratio and 90% C. I. (**Table 36**). In addition, a stratified Cox regression model adjusted for covariates will be applied to verify the impact of the prognostic factors on the treatment effect (**Table 36**).

Coding for treatment arm, stratification variables and prognostic factors is identical to that presented in **Section 7.5.1**.

Some patients received other anti-cancer therapy before progression or death. Sensitivity analyses will be performed by censoring those who have received anti-cancer therapy prior to documentation of disease relapse/progression or death on the earliest date cancer treatment began or treating them as having PFS events at the earliest date when the treatment began.

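### SAP 7.8 draws post-progression anti-cancer therapy (Table 60) only from the Short Follow-up Report, so Arm 2 therapy started between progression and the 4-week post-treatment visit can be misplaced or dropped

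*SAP*

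**What the plan says.** SAP 7.8 defines two rows of Table 60 that compare the arms on other anti-cancer treatment. The first is "Anti-cancer treatments before progression (reported on Treatment Report 4-Week Post-Treatment Follow-Up Report, and Follow-up Report for patients on DURVA+TREME Arm", with the Best Supportive Care Report as the source for BSC. The second is "Anti-cancer treatments for all patients after progression (reported on Short Follow-up Report), by treatment group". Neither the text nor the table shell compares a treatment start date with a progression date. A third block covers therapy on study drug or in the 4 weeks after it. It is for Arm 2 only, with BSC marked not applicable, and draws on the Treatment and 4-Week Post-Treatment reports.

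Protocol Appendix IV sets when each form is due. The Treatment Report is due "Every 4 weeks (28 days) while patient is on protocol treatment". The 4-Week Post-Treatment report is due "4 weeks from the date of last infusion". The Best Supportive Care Report and the Arm 2 Follow-up Report share one schedule: "Every 4 weeks (28 days) until objective progression". The Short Follow-up Report is 12-weekly once progression has occurred.

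Protocol 5.2 times the post-treatment visit at "4 weeks after end of last cycle date". It requires the visit for every Arm 2 patient and gives it a column under follow-up after objective progression.

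**The concern.** A form separates therapy before progression from therapy after it only if the form starts or stops at progression. Two of the three Arm 2 forms listed for the pre-progression row do not. A patient who stops drug because of progression still files the 4-Week report, and Protocol 10.3 leaves further treatment to the investigator from the moment protocol treatment stops.

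This matters because the trial is open-label with OS as primary endpoint, and Table 60 is the SAP's between-arm tabulation of later therapy. Protocol 4.1.6 and 4.1.7 allow patients to enter without prior regorafenib or TAS-102, so some could receive them afterwards. The protocol background credits those agents with median OS gains of 2.5 and 1.8 months, and SAP section 5 powers the trial for a 2.4-month difference. A reader judging an OS result will want to know whether the arms differed in such therapy. An Arm 2 count that is too low makes an OS gain look less attributable to later treatment.

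**Working it through.** The plan states no figure on this point. The check sets the forms side by side and then works out the timing.

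| Form | Arm | Ends or starts at progression? | Table 60 before/after row fed |
|---|---|---|---|
| Best Supportive Care Report | 1 | Ends at it | Before |
| Treatment Report | 2 | No; follows treatment | Before |
| 4-Week Post-Treatment report | 2 | No; follows end of treatment | Before |
| Follow-up Report | 2 | Ends at it | Before |
| Short Follow-up Report | Both | Starts after it | After |

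**Route 1, the 4-Week report (main route).** An Arm 2 patient progresses, stops drug, starts a new agent, and reports it at this visit. There are two readings of SAP 7.8:
- If the forms define the period, the entry goes in the pre-progression row.
- If dates define the period and the forms are only sources, the entry is rightly kept out of the pre-progression row. It also misses the post-progression row, because this form is not a source for it.

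Under both readings the post-progression row is one patient short, unless the therapy is entered again on the Short Follow-up Report. The documents do not require that, and the forms themselves are not included.

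**Route 2, the Treatment Report (narrow).** Protocol 7.1.7 says of a patient with RECIST progression that "the patient may remain on study therapy pending their next disease assessment", so Treatment Reports can be filed after progression. Protocol 7.2.2 bars other anti-cancer therapy on protocol treatment apart from local palliative radiation, so radiation is about all that can enter this way.

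**Length of the window.** Dosing is every 4 weeks and scans are every 8 weeks from randomization. Take progression on the week-8 scan, with drug stopped then:
- Week-8 dose not given: last infusion at week 4, cycle ends at week 8. The visit falls at 4 + 4 = week 8 by Appendix IV (window about 0 weeks), or 8 + 4 = week 12 by the 5.2 flowsheet (window 4 weeks).
- Week-8 dose given: last infusion at week 8, cycle ends at week 12. The visit falls at week 12 (window 4 weeks) or week 16 (window 8 weeks).

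The two protocol timings differ by one cycle and need reconciling; the window depends on which is followed.

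**BSC.** The Best Supportive Care Report covers 4-week periods, so therapy started after progression but within the same period could appear on it. The exposure there is limited to what remains of that one period.

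**Illustrative size.** Let f be the assumed share of the 120 planned Arm 2 patients who start therapy in the window and do not report it again. Patients missing from the post-progression row = 120 × f:
- f = 5%: 6
- f = 10%: 12
- f = 20%: 24

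The row is short by 100 × f percentage points. With 60 BSC patients, one misfiled BSC patient moves that arm's row by 1/60 = 1.7 points, against 1/120 = 0.8 points per patient in Arm 2.

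**The case against.** The strongest reply is that timing relative to progression is the stated criterion and the forms, given in parentheses, are only where the data sit. Where the SAP means a form to define a period it says so, as for on-treatment adverse events in 7.7.1. The PFS sensitivity analyses in 7.6.3 already work by date, handling "anti-cancer therapy prior to documentation of disease relapse/progression or death on the earliest date cancer treatment began". This has force: the documents do not settle that misfiling into the pre-progression row will occur. It does not rescue the post-progression row, whose only named source is the Short Follow-up Report.

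Second, the Arm 2-only block of Table 60 does display therapy given on drug or within 4 weeks after it. That is so, and the information is not lost from the report. But that block has no BSC column and does not split by progression, so it cannot repair the comparison.

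Third, eligibility criterion 4.1.8 requires best supportive care to be the only standard option left, which argues against assuming frequent, rapid next-line therapy. This stands, and is why no size can be claimed.

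A reader might infer several stronger points that the documents do not support:
- That BSC is free of the error. Its 4-weekly form allows some misfiling.
- That the window is always 4 or 8 weeks. Those intervals run from last infusion; from progression the window can be about zero.
- That an Arm 2 pre-progression count would look like a breach of Protocol 7.2.2. That section restricts therapy only while protocol treatment is being given, so therapy after stopping and before progression is allowed.
- That Table 61 mislabels its Arm 2 window. Its shell describes that window correctly; the problem is that the 7.8 text describes it differently.

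**Conclusion.** The concern holds in limited form. As written, SAP 7.8 leaves Arm 2 therapy that starts after progression and is recorded on the 4-Week report (or, narrowly, on a Treatment Report filed past progression) either in the wrong between-arm row or in neither. The likely direction is that later therapy in Arm 2 is understated relative to BSC, because BSC has only its last reporting period in which to misfile.

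The size cannot be determined from the documents. The 6 to 24 patients shown rest on assumed rates of 5% to 20% and on no re-reporting, and should not be read as an estimate of a between-arm gap. Table 60 is descriptive: the stratified log-rank test for OS and the date-based PFS sensitivity analyses do not depend on it. The case for changing it is that readers will use it to interpret OS and that correcting it costs little.

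**What to change.** For the before- and after-progression rows of Table 60, replace the form lists in SAP 7.8 with one rule for both arms: pool anti-cancer therapy entries from all report forms, remove duplicates within patient, and classify each entry by its start date against the date of first objective progression on the Relapse/Progression Report. Keep the Arm 2-only on-treatment block as it is.

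Separately, align the 7.8 text on major medical problems, which describes both arms as before progression, with the Table 61 shell, which uses on treatment or within 4 weeks after it for Arm 2 and before progression for BSC.

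The cost is a few sentences in the SAP and a date comparison in the table program. No new data should be needed, since the PFS sensitivity analyses in 7.6.3 already call for therapy start dates and the progression date is already collected.

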7.9 Quality of Life

The quality of life of patients in this study is assessed at 4, 8, 12, 16 and 24 months from randomization by using EORTC QLQ-C30 (version 3.0). The following are the scoring algorithms for this instrument.

7.9.1 EORTC QLQ-C30

The EORTC core questionnaire, QLQ-C30 (version 3.0), consists of five Functional Scales, Global Health Status, and nine Symptoms Scales. Each scale in the questionnaire will be scored (0 to 100) according to the EORTC recommendations in the EORTC QLQ-C30 Scoring Manual. The scoring method is summarized below. In this summary Qi refers to the ith question on the QLQ-C30.

Functional scale’s scores:

- Physical functioning: $(1 - ((Q1+Q2+Q3+Q4+Q5)/5 - 1)/3) * 100$
- Role functioning: $(1 - ((Q6+Q7)/2 - 1)/3) * 100$
- Emotional functioning: $(1 - ((Q21+Q22+Q23+Q24)/4 - 1)/3) * 100$
- Cognitive functioning: $(1 - ((Q20+Q25)/2 - 1)/3) * 100$
- Social functioning: $(1 - ((Q26+Q27)/2 - 1)/3) * 100$

Global health status score:

- Global health status/QOL: $((Q29+Q30)/2 - 1)/6 * 100$

Symptom scale's scores:

- Fatigue: $((Q10+Q12+Q18)/3-1)/3 * 100$
- Nausea and vomiting: $((Q14+Q15)/2-1)/3 * 100$
- Pain: $((Q9+Q19)/2-1)/3 * 100$
- Dyspnea: $(Q8-1)/3 * 100$
- Insomnia: $(Q11-1)/3 * 100$
- Appetite loss: $(Q13-1)/3 * 100$
- Constipation: $(Q16-1)/3 * 100$
- Diarrhea: $(Q17-1)/3 * 100$
- Financial difficulties: $(Q28-1)/3 * 100$

Missing items in a scale will be handled by the methods outlined in the scoring manual. In particular, values will be imputed for missing items by “assuming that the missing items have values equal to the average of those items which are present” for any scale in which at least half the items are completed. A scale in which less than half of the items are completed will be treated as missing.

7.9.2 Data Sets

The analyses of quality of life data will be restricted to randomized patients who have a measurement at baseline and at least one measurement after baseline.

The QOL assessment is performed prior to randomization and during chemotherapy/BSC at 4, 8, 16, and 24 weeks from randomization. Since exact time of assessment may vary from subject to subject, it is necessary to provide a window for each QOL time point. What follows is a description of how to assign a questionnaire to a discrete time point:

Time Point	Windows (i.e., time periods)
Baseline	14 days prior to up to the day of randomization
Week 4	2 weeks - < 6 weeks
Week 8	6 weeks - < 10 weeks
Week 12	10 weeks - < 14 weeks
Week 16	14 weeks - < 20 weeks
Week 24	20 weeks - < 28 weeks

If more than one questionnaire is available for the baseline window, then the latest non-missing measurement, per question, will be considered. If more than one questionnaire is available at a time point other than baseline, then the average (per question) of the non-missing measurements will be used.

Summary statistics, plots and longitudinal comparisons will be based on changes of the quality of life scores from baseline.

